3.1 Primary Objective

To compare postoperative changes in accommodative amplitude between patients undergoing unilateral lateral rectus recession combined with medial rectus resection and those undergoing unilateral lateral rectus recession combined with medial rectus plication.

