3.2 Secondary Objectives

- To compare postoperative ocular alignment between the two surgical groups.
- To compare surgical success at postoperative month 3 between the two surgical groups.
- To evaluate time-dependent changes in accommodative amplitude during postoperative follow-up.

4. Study Design

This is a prospective, interventional, non-randomized, parallel-group comparative clinical study conducted at a single tertiary ophthalmology center. Participants with primary exotropia were assigned to one of two surgical groups. The study compared unilateral lateral rectus recession plus medial rectus resection with unilateral lateral rectus recession plus medial rectus plication.

Participants were allocated using an alternating sequential allocation method according to the order of enrollment. The first participant who consented to participate was assigned to the LRR+MRR group, the second participant was assigned to the LRR+MRP group, and subsequent participants were assigned alternately thereafter. No random sequence generation, allocation concealment, or randomization procedure was used.

5. Study Population

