7.3 Postoperative Follow-up

Follow-up examinations were performed at postoperative week 1, postoperative month 1, and postoperative month 3. At each visit, best-corrected visual acuity, ocular motility, primary position deviation angle, and accommodative amplitude were recorded.

8. Outcome Measures

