8.1 Primary Outcome Measure

Change in accommodative amplitude: Accommodative amplitude was measured separately in each eye using the minus lens method. Measurements were performed before surgery and at postoperative week 1, postoperative month 1, and postoperative month 3. Changes were calculated by comparing postoperative values with the baseline preoperative value and were recorded in diopters.

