8.2 Secondary Outcome Measures

- Ocular alignment: Ocular deviation in primary position was measured using the prism and alternate cover test. Distance and near deviation angles were recorded in prism diopters at baseline and during postoperative follow-up.

- Surgical success: Surgical success was assessed at postoperative month 3 and was defined as ocular deviation in primary position of 10 prism diopters or less of exotropia or 5 prism diopters or less of esotropia.

9. Sample Size

A prior sample size calculation was performed based on the expected between-group difference in operated-eye change in accommodative amplitude from baseline to postoperative week 1, which was considered the primary functional outcome for sample size planning. Assuming a two-sided alpha level of 0.05, 80% power, an anticipated mean difference of 0.7 diopters, and a common standard deviation of 0.97 diopters, the minimum required sample size was estimated to be 31 patients per group. To allow for possible loss to follow-up, at least 36 patients were considered necessary in each group. The final analysis included 85 patients: 40 in the LRR+MRR group and 45 in the LRR+MRP group.

10. Statistical Analysis Plan

All statistical analyses will be performed using IBM SPSS Statistics version 28.0. Continuous variables will be assessed for normality using the Shapiro-Wilk test. Normally distributed continuous variables will be presented as mean \pm standard deviation. Non-normally distributed continuous variables will be presented as median and range. Categorical variables will be presented as number and percentage.

Between-group comparisons of continuous variables will be performed using the Mann-Whitney U test when variables are not normally distributed. Comparisons among more than two independent groups will be performed using the Kruskal-Wallis test. Repeated measurements within groups will be analyzed using the Friedman test. When significant differences are identified in repeated-measure analyses, pairwise comparisons will be performed using the Wilcoxon signed-rank test with Bonferroni correction.

Associations between categorical variables will be evaluated using the Pearson chi-square test or Fisher exact test, as appropriate. A two-sided p value less than 0.05 will be considered statistically significant.

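### The within-arm pairwise step names neither its comparisons nor its divisor, and single-step Bonferroni behind a Friedman gate is more conservative than it needs to be

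*Combined protocol and SAP*

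**What the plan says.** Section 10 (Statistical Analysis Plan) sets out a two-step procedure within each arm. First, "Repeated measurements within groups will be analyzed using the Friedman test". Then, on the condition "When significant differences are identified in repeated-measure analyses", it says "pairwise comparisons will be performed using the Wilcoxon signed-rank test with Bonferroni correction". No list of pairs and no divisor follows, and the sentence does not say which eye is tested.

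Section 8.1 fixes the visits: "Measurements were performed before surgery and at postoperative week 1, postoperative month 1, and postoperative month 3". It defines the outcome against baseline: "Changes were calculated by comparing postoperative values with the baseline preoperative value and were recorded in diopters".

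Two objectives bear on this. Section 3.1 is a between-group aim: "To compare postoperative changes in accommodative amplitude between patients undergoing unilateral lateral rectus recession combined with medial rectus resection", set against the plication arm. Section 3.2 adds a time-course aim: "To evaluate time-dependent changes in accommodative amplitude during postoperative follow-up". The last part of Section 10 places change both within and between groups in the main comparative analysis.

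**The concern.** The outcome in Section 8.1 consists of three contrasts: week 1, month 1 and month 3, each against baseline. The procedure in Section 10 is not written as those three contrasts. If pairwise means every pair of visits, as it usually does after a Friedman test, three further comparisons between postoperative visits share the correction. The threshold for the baseline contrasts is then half of what it would be for the three alone.

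Two further features cost power whichever family is meant. Single-step Bonferroni is never more powerful than Holm on the same tests. The Friedman condition also adds a hurdle that a Bonferroni or Holm procedure does not need for error control.

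What is at stake is the within-arm part of the main analysis and the time-course objective in Section 3.2. Leaving the divisor open also means that 3 or 6 could be chosen after the p-values are known.

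**Working it through.** **Inputs from the documents.** Four measurement times (8.1); two-sided alpha 0.05, difference 0.7 D, SD 0.97 D (Section 9); 40 and 45 patients analysed (Section 9).

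**The plan's own figure.** n per group = 2 × (1.960 + 0.842)² × 0.97² / 0.7² = 30.1, rounded up to 31. The stated 31 reproduces. It concerns the between-group difference in operated-eye change at week 1, not the within-arm tests.

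**Thresholds.** Pairs among four visits: 4 × 3 / 2 = 6, of which 3 involve baseline.
- Bonferroni over six: 0.05/6 = 0.0083.
- Bonferroni over three: 0.05/3 = 0.0167.
- Holm over three: 0.0167, then 0.025, then 0.05.

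**Effect of the divisor alone.** Paired t-test, SD of change 0.97 D, noncentrality = change × √n / 0.97 (for 0.5 D and n = 40: 0.5 × 6.32 / 0.97 = 3.26).

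| True change | n = 40, 0.0083 | n = 40, 0.0167 | n = 45, 0.0083 | n = 45, 0.0167 |
|---|---|---|---|---|
| 0.3 D | 22% | 31% | 26% | 35% |
| 0.4 D | 44% | 55% | 51% | 61% |
| 0.5 D | 68% | 77% | 75% | 83% |
| 0.7 D | 96% | 98% | 98% | 99% |

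The change detectable with 80% power is 0.56 against 0.52 D (n = 40), and 0.52 against 0.48 D (n = 45).

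**Whole procedure, by simulation.** Assumptions: normal data; independent visit residuals with SD 0.97/√2, so that each change has SD 0.97 D and changes correlate at 0.5; readings in 0.25 D steps; Wilcoxon tests with zeros dropped. Repeat runs differ by up to about 3 points. Power at week 1/month 1/month 3:

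| Scenario | Plan, read as gate + Bonferroni over six | Holm over six, no gate | Holm over three baseline contrasts, no gate |
|---|---|---|---|
| n = 40, losses 0.70/0.50/0.35 D | 93/64/30% | 96/70/38% | 98/80/55% |
| n = 45, same losses | 96/71/35% | not tabulated | 99/87/62% |
| n = 40, losses 0.50/0.35/0.20 D | 58/28/7% | not tabulated | 76/46/20% |

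**Where the gain comes from.** In one matched set of runs (n = 40, first scenario), month-3 power went from 29% (plan) to 40% (Bonferroni over three, no gate) to 57% (Holm over three). That is 11 points from the smaller family without the gate and 17 from the step-down. The gate alone costs about 0 to 3 points in this scenario, and up to about 6 at week 1 with the smaller losses.

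**Change at week 1 only.** Gate plus Bonferroni over six, against the three baseline contrasts at 0.0167 without a gate (continuous readings): n = 40: 18 against 29% (0.3 D), 62 against 74% (0.5 D), 94 against 97% (0.7 D). n = 45: 20 against 33%, 70 against 82%, 97 against 99%.

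**Error control.** With no true change, the chance of any false positive among the three baseline contrasts is about 1.2% under the plan and 4.0% with Holm over three. With some visits truly changed, the false-positive rate at each unchanged visit under Holm is 2 to 4%.

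**The case against.** The strongest reply is that the plan is valid as written. Friedman followed by Bonferroni-corrected Wilcoxon tests is a standard, conservative sequence that does not inflate type I error. That stands: this is lost efficiency and incomplete specification, not a false-positive problem.

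A reader might infer four stronger claims, and the documents do not support them.
- *That the plan fixes the correction at six tests.* It does not say so. Six is the natural reading, but the firm defect is that the family is unstated.
- *That the between-visit pairs are wasted.* They lie outside the outcome in 8.1, but week 1 to month 1 and month 1 to month 3 bear on recovery, which the time-course objective in 3.2 can cover. Dropping those tests would be a trade-off.
- *That the plan's strictness buys no error control.* Bonferroni over six protects six hypotheses and Holm over three protects three, so part of the gain in that comparison comes from a smaller family. Holm over all six avoids this criticism and still gains 3/6/8 points (96/70/38 minus 93/64/30).
- *That the trial's main question is compromised.* The objective in 3.1 and the sample size concern the between-group difference, which this step does not touch.

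It is also fair to say that the size depends on the assumed pattern. Holm's month-3 gain relies largely on the earlier visits being rejected first, and for a 0.7 D change at week 1 only there is little to gain.

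**Conclusion.** The point holds as one of specification and efficiency. Section 10 should name its comparisons and divisor, and its correction can be improved at no cost in familywise error. Holm over the same six pairs, without the gate, rejects everything the gated Bonferroni rejects and keeps the 5% limit. That statement needs no assumption about effect sizes.

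The numerical gain does rest on assumptions. The documents give no expected within-arm loss and no correlation between visits. The 0.7 D in Section 9 is a between-group difference. The 0.97 D there belongs to the between-group calculation for week 1, and its use for within-arm change at all three visits is assumed. On that basis the loss of power matters for within-arm changes of about 0.2 to 0.5 D and is small (1 to 3 points) for 0.7 D at week 1 only. Saying that real changes will be missed goes too far; they are more likely to be missed.

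**What to change.** Replace the Friedman and pairwise sentences in Section 10 with text to this effect:

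> Within each arm, operated-eye amplitude at week 1, month 1 and month 3 is compared with the preoperative value by three Wilcoxon signed-rank tests with Holm adjustment (familywise 5%). The three comparisons between postoperative visits form a separate, secondary family for the time-course objective, also Holm-adjusted at 5%. Neither family depends on the Friedman result.

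If a single error limit over all comparisons is preferred, use Holm over all six pairs without the gate, and say so.

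The cost is a few lines of text and no new data. The downside of two families is that the 5% limit holds within each family and not across all six tests.

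Timing matters. The study period ended in July 2025 and the document is dated 15 August 2025. The change should therefore be dated. If within-arm results have already been seen, it should be labelled post hoc and the results under both corrections reported.

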The main comparative analysis will evaluate postoperative changes in accommodative amplitude within and between the LRR+MRR and LRR+MRP groups. Secondary analyses will compare ocular alignment and surgical success between groups. Age-stratified analyses may be performed using predefined age categories of 5-12 years, 13-19 years, and 20-40 years, with delta accommodative amplitude used to minimize the effect of age-related baseline differences in accommodation.

11. Ethical Considerations

The study was conducted in accordance with the principles of the Declaration of Helsinki and was approved by the Clinical Research Ethics Committee of Basaksehir Cam and Sakura City Hospital. Written informed consent was obtained from all participants and/or their legal guardians before enrollment. Participation did not change the standard clinical indication for surgery, and both surgical techniques are established procedures used in the management of horizontal strabismus.

12. Data Management and Confidentiality

Study data were collected from ophthalmologic examinations and postoperative follow-up assessments. Data were recorded in a deidentified research dataset for analysis. No names, direct identifiers, or individual participant identifiers are included in this public protocol document.

13. Individual Participant Data Sharing Statement

Individual participant data will not be shared because no specific data-sharing plan was included in the study protocol or informed consent documents.

14. Safety Considerations

Both interventions are standard surgical procedures for horizontal strabismus. Postoperative clinical assessments included best-corrected visual acuity, ocular motility, ocular alignment, and clinical examination. Patients requiring further management after completion of the study follow-up were treated according to routine clinical practice. Patients with residual exotropia of 12 prism diopters or more at postoperative month 3 were scheduled for additional surgery in the fellow eye after completion of the study follow-up period.

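### The main comparative analysis mixes within-arm and between-arm tests without saying which decides, although the primary objective and sample size are between-group

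*Combined protocol and SAP*

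**What the plan says.** Section 10 of the combined protocol and SAP describes the main analysis in one sentence: "The main comparative analysis will evaluate postoperative changes in accommodative amplitude within and between the LRR+MRR and LRR+MRP groups". No order of priority follows.

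The methods in Section 10 are of two kinds:

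- **Within arms:** "Repeated measurements within groups will be analyzed using the Friedman test". If that is significant, Bonferroni-corrected Wilcoxon signed-rank tests compare pairs of visits. The number of pairs is not given.
- **Between arms:** Mann-Whitney U for non-normal data. No between-group test is named for normal data.

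The rest of the document points to a between-group question. Section 3.1 begins: "To compare postoperative changes in accommodative amplitude between patients undergoing unilateral lateral rectus recession combined with medial rectus resection", and the comparator is the plication arm. Section 9 bases the sample size on the "expected between-group difference in operated-eye change in accommodative amplitude from baseline to postoperative week 1". Change over time appears separately as a secondary objective in Section 3.2: "To evaluate time-dependent changes in accommodative amplitude during postoperative follow-up".

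**The concern.** A significant fall in accommodative amplitude in one arm and a non-significant fall in the other is not evidence that the arms differ. Each within-arm p value asks whether that arm changed from its own baseline. Neither uses the difference between the arms, which is what Section 3.1 asks about.

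Because both kinds of test sit under the main comparative analysis with no ranking, the plan does not exclude reading a split pair of within-arm results as a technique effect. The rationale in Section 2, that plication may better spare the anterior ciliary vessels, makes a fall after resection with none after plication a natural story to tell. The gap has a practical side too: if the change scores pass the Shapiro-Wilk test, Section 10 names no between-group test for them, while the within-arm tests remain fully named.

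**Working it through.** **Inputs from Section 9:** "Assuming a two-sided alpha level of 0.05, 80% power"; "an anticipated mean difference of 0.7 diopters"; "a common standard deviation of 0.97 diopters"; stated minimum 31 per group; 40 and 45 analysed. **Assumption:** the true change common to both arms, which the documents do not give, is varied from 0 to 0.7 D.

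**Step 1: the plan's own figure.** n per group = 2 × (1.960 + 0.842)² × (0.97/0.7)² = 2 × 7.85 × 1.920 = 30.1, rounded up to 31. The stated figure reproduces, and it is a between-group calculation.

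**Step 2: power of the between-group test at the analysed size.** SE = 0.97 × √(1/40 + 1/45) = 0.211 D. 0.7/0.211 = 3.32, and Φ(3.32 − 1.96) = 0.913. The t-test version gives 0.907.

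**Step 3: split significance when the techniques are identical.** For one arm, power p comes from the noncentral t distribution with noncentrality d/(0.97/√n) and n − 1 degrees of freedom. The arms are independent, so P(exactly one significant) = p₁(1 − p₂) + p₂(1 − p₁).

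Example at d = 0.3 D, alpha 0.05: p₁ = 0.479 (n = 40) and p₂ = 0.528 (n = 45). 0.479 × 0.472 + 0.528 × 0.521 = 0.226 + 0.275 = 0.501.

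Four visits give 4 × 3/2 = 6 pairs, so 0.05/6 represents Bonferroni over all pairs.

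**Step 4: simulation of the planned sequence** (2000 runs per row). Assumptions: independent visit errors with SD 0.97/√2, so that change has SD 0.97 D; a fall of d at week 1, 0.5d at month 1 and 0.2d at month 3. The Wilcoxon column is week 1 against baseline after a significant Friedman test, Bonferroni over 6 pairs.

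| Common change d (D) | Split, single test at 0.05 | Split, single test at 0.05/6 | Split, Friedman (sim.) | Split, Wilcoxon (sim.) | Mann-Whitney on week-1 change: false positives (sim.) |
|---|---|---|---|---|---|
| 0 | 9.5% | 2% | 9% | 1% | 4% |
| 0.1 | 18% | 5% | – | – | – |
| 0.2 | 39% | 16% | 23% | 10% | 4% |
| 0.3 | 50% | 37% | 44% | 30% | 5% |
| 0.4 | 38% | 50% | 49% | 46% | 6% |
| 0.5 | 17% | 41% | 42% | 49% | 5% |
| 0.6 | 5% | 20% | 21% | 28% | 4% |
| 0.7 | 1% | 6% | 7% | 11% | 5% |

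**Step 5: the reverse error.** With a true difference of 0.7 D, the split rate in the Wilcoxon tests depends on where the two falls lie, not on their difference:

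| Falls (D), first arm vs second | Split, Wilcoxon | Mann-Whitney power |
|---|---|---|
| 0.7 vs 0 | 92% | 90% |
| 1.2 vs 0.5 | 33% | 88% |
| 1.7 vs 1.0 | 0% | 88% |

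In the last row both arms are significant in essentially every run, so the within-arm tests show no contrast at all.

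**The case against.** The strongest reply is that the plan already holds a valid comparison and nowhere says it will infer a technique effect from within-arm results. Much of this stands, and it rules out several stronger readings.

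- **Equal weight.** A reader might infer that Section 10 gives both parts the same standing. It names both and ranks neither, while Sections 3.1 and 9 lean towards the between-group comparison. The defect is the missing hierarchy, not a stated equality.
- **No group-by-time test.** A reader might conclude that nothing compares the courses. Section 8.1 defines the outcome as change from baseline, and a between-group test of that change is the group-by-time contrast for that visit. For non-normal data Section 10 supplies one, and the simulation shows that it holds its error rate. Only a single omnibus interaction test is absent.
- **The time-course objective.** It might be read as needing a between-group analysis. The other two objectives in Section 3.2 speak of comparing the groups; this one does not, so within-arm tests are a fair match for it.
- **Unequal arms.** The 40 versus 45 split might seem to drive the discordance. With power 0.479 in both arms, the rate at 0.3 D would be 2 × 0.479 × 0.521 = 49.9%, against 50.1%.
- **Split results as the rule.** The 50% figure is not the trial's false-positive rate, because the plan states no rule that decides on discordance. It also comes from an uncorrected single test; the simulated Wilcoxon sequence gives 30% at the same 0.3 D.

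What remains is that the plan neither makes the between-group test decisive nor bars comparative inference from the within-arm tests.

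**Conclusion.** The concern holds as a gap in the hierarchy of analyses. Within-arm tests stand inside the main comparative analysis unranked, and they cannot answer the primary question. If a technique difference were read from them, identical techniques would give split results in up to about half of trials. That rate needs a common change of roughly 0.2 to 0.6 D, depending on the test; it is below 10% at 0 D and about 11% or less at 0.7 D. A true 0.7 D difference could also go unseen if both arms fall clearly.

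These sizes rest on the Section 9 SD applying to change in each arm, on an assumed common change, and, for the simulated columns, on the assumed visit profile and independent visit errors. That within-arm tests do not test a difference between arms rests on none of these. The improvement is worthwhile and cheap; the planned between-group comparison is not invalid.

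**What to change.** In Section 10:

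1. Name the between-group difference in operated-eye change at week 1, the quantity behind the sample size, as the sole decisive comparison. Report the estimate with a 95% CI.
2. Adjust it for baseline amplitude and age, both already collected. ANCOVA is enough. SPSS MIXED with group, visit, group-by-visit, baseline amplitude and age would also give the month 1 and month 3 differences. Either removes the gap for normally distributed data.
3. Keep the Friedman and Wilcoxon tests as secondary, descriptive analyses for the time-course objective, and state that no technique difference will be inferred from them.
4. Keep the Mann-Whitney test on change as a sensitivity analysis.

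The cost is wording and one model in the software already named; the sample size does not change. There are two downsides. Within-arm p values lose inferential status. And because the document is dated 15 August 2025, after a study period ending in July 2025, the model cannot be presented as fixed before data collection. It should be dated and reported as specified on that date.

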5.1 Inclusion Criteria

- Patients aged 5 to 40 years.
- Diagnosis of basic primary exotropia.
- Stable deviation angle over three consecutive preoperative visits.
- Deviation angle of at least 20 prism diopters.
- Literacy and cooperation sufficient to perform accommodative amplitude testing.
- Agreement to undergo unilateral horizontal strabismus surgery.
- Written informed consent obtained from the participant and/or legal guardian.

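### Alignment and surgical success are compared by unadjusted tests alone, with no between-arm difference, no confidence interval and no use of the preoperative angle

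*Combined protocol and SAP*

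**What the plan says.** Section 3.2 makes postoperative alignment and month-3 surgical success secondary objectives. Section 10 covers them in one sentence: "Secondary analyses will compare ocular alignment and surgical success between groups". The methods come from the general paragraphs of the same section:

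- Continuous outcomes: "Between-group comparisons of continuous variables will be performed using the Mann-Whitney U test when variables are not normally distributed". No between-group test is named for normally distributed data.
- Binary outcomes: "Associations between categorical variables will be evaluated using the Pearson chi-square test or Fisher exact test, as appropriate".
- Decision rule: "A two-sided p value less than 0.05 will be considered statistically significant".
- Descriptive reporting: means with SDs or medians with ranges for continuous data, and "Categorical variables will be presented as number and percentage".

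Section 8.2 fixes success at month 3, "defined as ocular deviation in primary position of 10 prism diopters or less of exotropia or 5 prism diopters or less of esotropia". For alignment it says "Distance and near deviation angles were recorded in prism diopters at baseline and during postoperative follow-up". It does not say which visit is compared, or whether the raw angle or its change is used.

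The starting angle is bounded only from below in Section 5.1: "Deviation angle of at least 20 prism diopters". Section 7.1 has it measured on at least three preoperative visits. Sections 6.1 and 6.2 state that the preoperative distance angle set the surgical dosage in each arm. Section 4 describes alternating allocation by enrolment order, without concealment or randomisation, and mentions no stratification.

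**The concern.** Two things are missing from the analysis of the surgical outcomes.

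**An estimate with its uncertainty.** Group summaries are planned, but the between-arm inference consists of a p value. The only sample size calculation (Section 9) concerns week-1 change in accommodation, so nothing in the plan speaks to precision for success. A report that success did not differ significantly would leave the reader unable to see how large a difference remains possible.

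**The baseline value of the outcome.** Alignment is the same quantity measured before and after surgery, yet the preoperative value is not used in the between-arm comparison. The plan does address baseline differences for accommodation, through the change score in its age-stratified analyses, but makes no similar provision for the deviation angle. Because allocation was predictable and not stratified by angle, comparability of starting angles cannot be taken for granted.

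At stake is how the study's surgical comparison is read, alongside its primary question on accommodation.

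**Working it through.** **The plan's own figure.** Section 9 gives a difference of 0.7 D, SD 0.97 D, two-sided alpha 0.05 and 80% power. n = 2 × (1.96 + 0.8416)² × 0.97² / 0.7² = 30.1, rounded up to 31 per group. The stated 31 reproduces, but it concerns accommodation only. No corresponding figure exists for alignment or success.

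**Precision for success.** Inputs: 40 and 45 analysed patients (Sections 1 and 9). The documents give no success rate, so a common rate p is assumed over a range.

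Half-width = 1.96 × √[p(1 − p)(1/40 + 1/45)], with 1/40 + 1/45 = 0.04722.

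| Assumed success, both arms | 95% half-width (points) | Power for a 10-point deficit | Deficit detectable with 80% power (points) |
|---|---|---|---|
| 60% | 20.9 | 15% | about 30 |
| 70% | 19.5 | 16% | about 30 |
| 80% | 17.0 | 18% | about 29 |
| 90% | 12.8 | 24% | about 25 |

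**Illustration with assumed counts.** 32/40 (80%) against 30/45 (67%) gives chi-square p = 0.17 and Fisher p = 0.22. The difference is 13.3 points, with a Newcombe 95% interval from −5.7 to +30.7. Under the plan this is a non-significant result with two percentages, although the data are compatible with a difference of about 30 points.

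**For scale.** Excluding a 10-point deficit at 80% success (one-sided 0.025, 80% power) would need about 252 patients per group. Excluding 15 points would need about 112.

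**How much a starting-angle imbalance could matter.** The SE of the baseline mean difference is √0.04722 = 0.217 SD. Chance alone therefore gives a 95% range of ±1.96 × 0.217 = ±0.43 SD, and a 36% probability of an imbalance above 0.2 SD. This is a difference in starting angle and has to be carried through to the outcome. Assume an angle SD of 8 to 12 prism diopters and a residual angle that rises 0.1 to 0.3 prism diopters per prism diopter of preoperative angle:

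- Low end: 0.1 × 0.2 × 8 = 0.16 prism diopters.
- High end: 0.3 × 0.43 × 12 = 1.55 prism diopters.

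Assume further that residual deviation is normal with mean 4 prism diopters of exotropia and SD 6 or 8. The probability of falling within the success limits is then 77.5% or 64.3%. A shift of 0.16 prism diopters (SD 8) lowers it by 0.2 points, one of 1.3 (SD 6) by 3.4 points, and one of 1.55 (SD 6) by 4.3 points. All of these are small beside the half-widths above.

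**Precision gain from adjustment.** If preoperative and postoperative angles correlate at 0.2, 0.3 or 0.5 (assumed), the residual variance falls to 1 − r² = 0.96, 0.91 or 0.75 of its unadjusted value.

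**The case against.** The strongest reply is that dosage was scaled to the preoperative distance angle in both arms, so surgery itself already acts on the covariate. This stands in part: it should weaken the dependence of the result on the starting angle, though nothing in the documents shows that it removes it.

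A reader might infer that an angle imbalance does bias the comparison. The documents do not support that. They report no baseline angles by arm, and chance imbalance is already reflected in the standard error of an unadjusted comparison, so it costs precision and is not bias. The route to bias is systematic imbalance, from predictable allocation or from removals after it (Section 5.2 lists loss to follow-up and incomplete examinations as exclusions). Strict alternation gives arms that differ by at most one. A split of 40 to 45 therefore means removals or departures from alternation, but the documents do not say which, and no size can be put on any resulting bias.

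A reader might also infer that the sponsor intends to claim equal success. No section plans or claims equivalence or non-inferiority. The risk lies in how a p value without an interval may be read.

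Nor does the plan fix a month-3 rank test for alignment. Month 3 is tied only to success, and the Mann-Whitney test only to non-normal data.

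Finally, the planned counts and percentages would let a reader compute the risk difference and its interval. That is true and makes this half an omission of reporting, with no information lost. It does not help with adjustment for the angle, which needs patient-level data.

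**Conclusion.** The point holds in a limited form. Section 10 plans no between-arm difference, interval or baseline adjustment for alignment or success, although the preoperative angle is already recorded.

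The missing interval is the weightier part. Half-widths of about 20, 17 and 13 points at assumed success of 70, 80 and 90% mean that non-significance could not be taken as similar success. The arm sizes are the documents' own; the success rates are assumptions.

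The missing adjustment probably has a modest effect: about 0.2 to 1.5 prism diopters in mean alignment and roughly 0.2 to 4 points in success, all under assumed SDs, slopes and residual distribution. Its value lies in precision and in protection against systematic imbalance. These are secondary outcomes and the remedy is cheap, so the change should be made, but the point does not touch the primary analysis.

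**What to change.** 1. **Alignment.** Analyse signed month-3 distance deviation by ANCOVA with arm and preoperative distance deviation, and near deviation likewise with its own baseline. Report the adjusted mean difference with a 95% CI. Use a robust or rank-based version if the residuals require it.
2. **Success.** Report the month-3 risk difference with a 95% CI, for example by Newcombe's method. Add a sensitivity analysis adjusted for preoperative distance deviation, by logistic regression with marginal standardisation. If failures are few, use a penalised fit: at 90% success only about 0.10 × 85 = 8.5 failures are expected, too few for an ordinary fit to be stable.
3. **Interpretation.** State that p > 0.05 will not be read as equivalence, since no margin was set and the study was not sized for one.
4. **Status.** The study period ended in July 2025, and the document, dated 15 August 2025, already gives the final analysed numbers. If outcome data have been analysed, label these analyses post hoc.

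The cost is a short SAP revision and a few models on data already collected. The drawback is possible post hoc status. The success interval will stay wide, because its width follows from the 85 patients; the gain is that the reader sees it.
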